12.1. Response criteria

Response criteria are defined according to the Revised Recommendations of the International Working Group for Diagnosis, Standardization of Response Criteria, Treatment Outcomes and Reporting Standards for Therapeutic Trials in Acute Myeloid Leukemia [29].

12.2. Definition of Study Endpoints

12.2.1. Primary endpoint

=> Relapse Free Survival (RFS), 50 events (relapse)

RFS is defined as time interval from randomization until relapse of AML or death from any cause, whichever ever occurs first. Relapse is defined as any blast appearance in the peripheral blood, in the bone marrow (> 5%) or extramedullary blasts (chloroma). For a patient with no relapse before the end of study follow-up, observation of RFS will be censored at the date of his or her last follow-up examination.

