11.2. Power and Sample Size Calculation

The primary endpoint of the study, relapse-free survival (RFS), is defined as the time interval from randomization until relapse or death from any cause, whichever occurs first. For a patient with none of these events before the end of study follow-up, observation of RFS will be censored at the date of his or her last follow-up examination. It is assumed that the RFS rate after 2 years may be increased from 65% with placebo (Gale et al., Blood 2005; Thiede et al., Blood 2006) to 82.5% with sorafenib, corresponding to a hazard ratio (HR) of 0.45. Comparing the sorafenib with the placebo group by a log-rank test at a two-sided alpha of 5%, 49 observed events are required to obtain a power of 80%. It is important to note that due to a decreasing likelihood of relapses over time, the Kaplan-Meier curve for RFS of Flt3-ITD AML patients after allo-SCT forms a plateau after around 2 years at the above-mentioned values.

Under these assumptions, 184 patients (i.e., 92 per group) are needed in order to observe 49 events after a minimum observation period of 24 months for each patient. The inclusion of a total of 200 patients in the study allows for compensation of a dropout rate of 8%. During the course of the study, it may be decided to adapt the number of included patients. If this is done based on a data inspection (rather than solely on the absolute number of events which occurred so far, irrespective of the study arm), the method for sample-size adaptation in survival trials developed by Schäfer and Müller (Schäfer H, Müller H-H. Modification of the sample size and the schedule of interim analyses in survival trials based on data inspections. Statist Med 2001;20:3741-3751) will be employed which ensures that the type I error risk is not affected. It may also be decided later to add one or more interim analyses using the adaptive method mentioned above, especially if the sample size is increased.

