11.3. Interim analysis

There will be an interim analysis of safety after 20 patients have been treated for at least 3 months. Numbers of adverse events will be analyzed descriptively as well as in comparison between the two study arms by means of Fisher's exact test. An interim data inspection will be performed during the first half of 2014 according to the method proposed by Schäfer and Müller (Statist Med 20:3741-3751, 2001), which will take into account all patients included in the SORMAIN trial so far. This will offer the study management the chance to adapt the total sample size while keeping the original type I error rate constant, that is, without increasing the risk of a false positive study result. The reasons for this interim data inspection, which

had not been explicitly planned but outlined in the study protocol (V03F, Section 11.2 Power and Sample Size Calculation, p.44) to be decided about later, are twofold:

- (1) The recruitment rate has been much lower than expected. Whereas 200 patients were planned to be recruited within an accrual period of 24 months, only 45 patients have been randomized after 40 months of accrual.
- (2) Based on accumulating evidence from controlled trials with AC220 and Midostaurin (both are new FLT3-ITD inhibitors) and clinical experience with sorafenib used outside of clinical studies in the AML indication, it is not unlikely that sorafenib therapy might generate a larger treatment benefit compared to placebo than the hazard ratio of 0.45 implies, which was originally assumed for the sample size calculation.

If the interim data inspection, which takes into account all available information regarding relapse or censoring events as well as treatment group allocation of patients, shows indeed a larger treatment difference than originally assumed, the additional number of events required before the final analysis, and hence the sample size, could be reduced. This would enable completion of the SORMAIN trial and a judgement of efficacy in less time and with a smaller number of patients.

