According to the method by Schäfer and Müller, the data obtained up to the time point of the interim inspection will be used to calculate the value of the log-rank test statistic. Given that value, the probability of falsely rejecting the null hypothesis of no treatment difference (conditional rejection error probability, CRP) at the originally planned study end point, that is, after a total number of 50 events, will be calculated using the formulae in the above-mentioned paper. The design of the remaining part of the trial can be changed to any other design, that is, to a different number of additional events up to the final analysis, with the log-rank test statistic finally being applied to the additional events and assuming a type I error rate equal to the CRP calculated at the interim inspection. It is allowed to use all information from the interim inspection, such as Kaplan-Meier curves and estimates of the treatment difference (hazard ratio), to recalculate the additional number of events required to obtain a given power, without the total type I error being compromised. It is even possible to apply a group-sequential design to the remaining part of the trial. Alternatively, it can be decided after the interim inspection to leave the trial design unchanged.

The preservation of the pre-specified type I error rate – in this trial a two-sided alpha of 0.05 – is guaranteed when applying the CRP principle if the interim data inspection is used for sample-size adaptation only but not for an interim analysis with the option to reject the null hypothesis of no treatment difference. It is hereby explicitly stated that the envisaged interim inspection will not be used to perform such an analysis, that is, no formal statistical test will be done at that interim time point with the chance to conclude that a significant treatment difference is present. In other words, no alpha will be spent at the interim inspection.

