In order to perform the interim data inspection, the trial biostatistician will receive the data regarding relapse and censoring events together with treatment group membership, that is, in a blinded fashion, without any further variables. The Coordinating Centre for Clinical Studies (KKS) Marburg will provide these data with new random ID numbers, such that the biostatistician can use as little information from the interim inspection as possible at later stages of the analysis, maintaining blinding to the largest possible degree. The results of the interim data inspection (log-rank test statistic, CRP given the test statistic, Kaplan-Meier curves, treatment difference in terms of hazard ratio) as well as recalculated power values assuming the CRP and various effect sizes will be communicated by the biostatistician only to the unblinded contact. The unblinded contact will communicate in an unblinded fashion with the DSMC members. The DSMC will decide about whether and how the design of the remaining part of the trial should be changed, e.g. the sample size reduced in case of an unexpectedly large treatment difference, or whether the trial should be stopped due to futility. This decision will be communicated in written form to the unblinded contact and the Steering Committee. If the design is modified, this will be specified in a further protocol amendment. The details of a design modification will be communicated to as few people involved in the performance of the trial as possible, in order to avoid that study personnel might draw conclusions about the observed treatment difference from the decision regarding the change of trial design.

11.4. *Statistical Analysis Plan*

The primary objective, RFS (as defined above), will be analyzed by means of the Kaplan-Meier method as well as the log-rank test at a two-sided alpha of 0.05 to test for differences between the two study arms. Possible sample size modifications or interim analyses will be performed according to the adaptive method by Schäfer and Müller as described in section 11.2.

Secondary endpoint of the study is overall survival (OS), defined as time from randomization to the day of death; for a patient who is not known to have died by the end of follow-up,

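### The protocol defines RFS as relapse or death, but words the main censoring rule, the 50-event target and the interim dataset for relapse only

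*Protocol*

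**What the plan says.** The definition is the same in the Synopsis, 4.2.1, 11.2 and 12.2.1. In 12.2.1 it reads: "RFS is defined as time interval from randomization until relapse of AML or death from any cause". The rules attached to it differ.

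- **Censoring in the Synopsis, 4.2.1 and 12.2.1:** "For a patient with no relapse before the end of study follow-up, observation of RFS will be censored" at the last follow-up examination. Death is not mentioned.
- **Censoring in 11.2:** "For a patient with none of these events before the end of study follow-up, observation of RFS will be censored". The events meant are relapse and death, named in the sentence before.
- **Event target in the Synopsis and 12.2.1:** "Relapse Free Survival (RFS), 50 events (relapse". Section 4.2.1 does not carry this label.
- **Event target in 11.3:** the conditional rejection probability (CRP) refers to the planned end "after a total number of 50 events", with no event type given.
- **Interim inspection in 11.3:** it "takes into account all available information regarding relapse or censoring events as well as treatment group allocation of patients". Later, "the trial biostatistician will receive the data regarding relapse and censoring events" with treatment group, and the text says that no other variables are supplied.
- **Final analysis in 11.4:** a log-rank test on RFS as previously defined, by intention to treat.

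**The concern.** A patient who dies in remission has an RFS event under the definition and under 11.2. Under the censoring sentence in the other three places, the same patient has no event and is censored at the last examination before death. A programmer or data manager working from 12.2.1 and one working from 11.2 would build different primary datasets.

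Three things are at stake:

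1. **The primary test.** Censoring deaths in remission changes the question from RFS to the cause-specific hazard of relapse. Death in remission is a competing event after transplant. Section 3.4 itself concedes limited experience with sorafenib's interference with graft-versus-leukaemia and graft-versus-host effects, and with its toxicity alongside post-transplant medication.
2. **The trigger.** A target of 50 relapses is not the target that the sample size was built to deliver.
3. **The adaptation.** Section 11.3 computes the interim log-rank statistic, hazard ratio and CRP from the transferred data, and the monitoring committee may change the sample size or stop for futility on them. The CRP argument needs the conditional error of the test that was actually planned.

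**Working it through.** **Inputs (protocol 11.2):** 2-year RFS 65% on placebo and 82.5% on sorafenib; stated hazard ratio 0.45; two-sided alpha 0.05; power 80%; 49 events; 184 patients (92 per group); 200 after allowing for 8% dropout. Allocation is 1:1 (5.5).

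**Step 1: reproduce the plan.**
- Hazard ratio = ln(0.825)/ln(0.65) = 0.4466, stated as 0.45.
- Schoenfeld events = 4 × (1.960 + 0.842)² / (ln HR)². With 0.4466 this is 48.3, so 49. With 0.45 it is 49.2, so 50. The 49 in 11.2 and the 50 elsewhere are one calculation with the hazard ratio unrounded or rounded.
- Events expected from 184 patients = 92 × 0.35 + 92 × 0.175 = 48.3.
- 184/0.92 = 200.

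All these figures come from RFS rates, so the plan was sized on relapse or death. If deaths count, no planning figure changes.

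**Step 2: apply the relapse-only label to the same sample.** Let f be the share of RFS events that are deaths in remission. The protocol gives no value, so 10 to 40% is assumed.
- Relapses among 184 = 48.3 × (1 − f).
- Patients needed for 50 relapses, before dropout = 50 / [0.2625 × (1 − f)], where 0.2625 is the mean of 0.35 and 0.175.
- Power if the relapse hazard ratio is also 0.45 = Φ(|ln 0.45| × √d / 2 − 1.960), with d the number of relapses.

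| f | relapses among 184 | patients for 50 relapses | power at HR 0.45 |
|---|---|---|---|
| 10% | 43.5 | 212 | 75% |
| 20% | 38.6 | 239 | 70% |
| 30% | 33.8 | 273 | 64% |
| 40% | 29.0 | 318 | 58% |

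Even with all 200 patients fully observed, events = 100 × 0.35 + 100 × 0.175 = 52.5, so 50 relapses need f of at most 1 − 50/52.5 = 4.8%. Longer follow-up would add little on the protocol's own terms, because 11.2 says the RFS curve reaches a plateau at around two years.

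**Step 3: the two stages of the adaptive test.** Suppose the interim statistic and CRP use relapses only and the later events include deaths.
- *Treatment affects neither relapse nor death.* In a simulation with 200 patients, interim at 20 relapses, CRP computed for 50 relapses, 30 further RFS events and 30% of events being deaths in remission (20,000 runs), the one-sided rejection rate was 0.027 against a nominal 0.025. The error rate is roughly kept.
- *RFS is equal in the two arms, but fewer relapses on sorafenib are offset by more deaths in remission.* The rejection rate was 0.091 in one such scenario (5,000 runs). The size depends on how large the offset is, so the figure is only illustrative.

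**The case against.** The strongest defence is that this is loose drafting around a clear definition. Every definition includes death. Section 11.2, the only full statement in the statistics chapter, censors correctly, and 11.4 points back to RFS as defined. Section 11.3 does not restrict its 50 events to relapse, and its references to relapse and censoring can be read as shorthand for RFS data. No section sets up relapse with death censored as an endpoint of its own. This stands: a reader might infer that deaths in remission are certain to be censored, and the protocol does not establish that. But the relapse-only wording appears in three censoring sentences, two event labels and two descriptions of the interim data. The last of these rules out further variables. That is too consistent to leave to interpretation.

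Three further inferences are tempting and not supported:

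- **That treatment-related mortality would be hidden.** Overall survival counts every death and is tested (11.4). Fatal events are SAEs (9.2), and the safety committee reviews all SAEs (13.1).
- **That censoring deaths necessarily makes the hazard ratio more favourable.** If deaths are the same share of events in each arm, it stays at 0.45. If 2-year non-relapse mortality is 5% in both arms, the relapse hazard ratio is 0.4466 × (0.125/0.175)/(0.30/0.35) = 0.37. Under that assumption the 184 × 0.2125 = 39 relapses would give about 87% power. The power column above therefore depends on its own assumption. The shortfall against 50 relapses appears under both.
- **That the type I error guarantee fails outright.** It fails only under the condition shown in step 3.

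**Conclusion.** The protocol contradicts itself on what counts as a primary-endpoint event, and this should be settled before interim data are used. The planning figures are sound for the composite and need no change.

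If the relapse-only wording were followed, deaths in remission would be censored in the primary or interim analysis. The 50-event trigger would then probably not be met: about 43 to 29 relapses among 184 patients, if 10 to 40% of RFS events are deaths in remission. That range is assumed, but the direction is not sensitive to it, since 184 patients give only about 48 events of both kinds together.

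If the interim statistic and CRP used relapses and the final test used RFS, the type I error guarantee in 11.3 would not be established for the RFS null when relapse and death in remission move in opposite directions. It would be roughly kept if treatment affects neither.

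**What to change.** 1. In the Synopsis, 4.2.1 and 12.2.1, replace the censoring sentence with the 11.2 rule: censor only patients with neither relapse nor death by the end of follow-up.
2. In the Synopsis and 12.2.1, change the target label to 50 RFS events (relapse or death from any cause). Reconcile it with the 49 in 11.2, so that one number stands throughout.
3. In 11.3, state that the interim transfer contains the date and type of first RFS event (relapse or death), or the censoring date, with treatment group. State that the interim log-rank statistic and the CRP are computed on RFS as defined in 11.2.

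The cost is wording edits in four places and one added variable in the interim transfer. No extra patients, visits or data are needed, because deaths are already collected for overall survival.

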12.2.2. Secondary endpoint

=> Overall Survival (OS)

OS is defined as time from randomization to the day of death. For a patient who is not known to have died by the end of follow-up, observation of OS will be censored on the date the patient was last known to be alive.

13. Quality Assurance

13.1. Data Safety Monitoring Committee

The Safety Committee of this trial will consist of three members of the scientific community not involved in this trial. The committee will be provided with a first safety analysis after 20 patients have been treated for at least 3 months and then yearly thereafter. The safety

meeting will be held by phone conference with the Principal Investigator, KKS and statistician of the trial and review all serious adverse events (SAE), suspected unexpected severe adverse reactions (SUSARS). The Safety committee will give recommendations about the continuation of the trial and/or about necessary trial amendments.

13.2. *Monitoring and inspection by authorities*

The monitoring of the study takes place by the trained staff of the KKS Marburg. Patient recruitment can begin after the initiation visit. During the course of the study each participating centre will be visited for monitoring.

During each of these visits, source data verification will be performed on the basis of a pre-specified sampling plan. The KKS Marburg will generate this plan. Furthermore, at these visits problematic cases will be discussed.

Source data verification will be performed by direct access to the original patient records and the monitoring organization (KKS) guarantees that patient confidentiality will be respected at all times. Participation in this study will be taken as agreement to permit direct source data verification. Data generated at the pre-screening visit are verified against source data only in case the patient enters the study.

In compliance with European regulations/ICH-GCP Guidelines, it is required that the investigator and institution permit authorized representatives of the study central office and the regulatory agency(s) direct access to review the subject's original medical records for verification of study-related procedures and data. Direct access includes examining, analyzing, verifying, and reproducing any records and reports that are important to the evaluation of the study. The investigator is responsible for giving any requested support for any monitoring, inspection or audit visit. The investigator has to be available during these visits.

13.3. *Data Management*

13.3.1. *Data entry*

The investigator is responsible for the performance of the trial in accordance to GCP guidelines and the study protocol as well as the correct data entry to the corresponding electronic case report form (e-CRF). The data of the patients are documented with the EDC (Electronic Data Capture) system MACRO™ which is hosted at KKS Marburg. The data are entered directly via web browser (Microsoft Internet Explorer 6.x or 7.x required or Microsoft Internet Explorer 8.0 run in compatibility mode) to the e-CRF and are transferred via high encryption (SSL 128-bit encryption) to the central database. Therefore, documentation on paper CRF is not necessary.

Detailed requirements for using EDC are specified in an EDC Manual which is part of the ISF.

In order to use the EDC system all staff who are entering and monitoring data are provided with training materials and required documentation by KKS Marburg. For training of data entry KKS provides a test database. All data which are collected during the trial have to be documented in the e-CRF by authorized persons according to the personnel log.

The EDC system has an implemented audit trail. This assures that any documentation and/or changes to database items are traceable anytime. Changes or corrections are permitted to persons who are documented in the TMF and who have access to the system with user specific access rights. This access is documented by KKS Marburg.

Users with monitoring function are not able to enter or change patient's data. They have the possibility to view the data write protected (review function) and they can create SDV marks in case of queries. Discrepancies which appear at data management are forwarded to the monitors or to the site directly.

13.3.2. Data concealment for electronic transfer

Every investigator, study nurse, monitor or other person involved in the trial receives his or her personal login data (username and password). Access rights to the database will depend on the group affiliation. Users of the EDC-System MACRO will receive the training materials by the data management of KKS Marburg. Every person who gets access to the system has to fill in a registration form (User-ID request) and has to confirm that they have been adequately trained.

Thus it is guaranteed that only authorized persons (TMF, personal log) have access to the system to enrol patients to the trial. The data are transferred via high encryption (128-bit, SSL) across the internet.

At the end of study, the database will be closed after data cleaning process. This process will be documented according to SOPs of KKS Marburg.

For analysis, the following software will be used:

SAS version 9 or more recent version, as well as statistics software package R (R Development Core Team (2009). R: A language and environment for statistical computing. R Foundation for Statistical Computing, Vienna, Austria. ISBN 3-900051-07-0, URL <http://www.R-project.org>).

14. Responsibilities, Ethical Considerations, Confidentiality, Insurance

14.1. Investigator's Responsibilities

The Principal Investigator has more than two years of experience in the conductance of clinical trials.

The investigator shall be responsible for ensuring that the clinical study is performed in accordance with the protocol, the ethical principles that have their origin in the Declaration of Helsinki (World Medical Association Declaration of Helsinki, 1996) as well as with the International Conference on Harmonization of Technical Requirements of Pharmaceuticals for Humans Use (ICH) Note for Guidance on Good Clinical Practice (ICH, Topic E6, 1995) approved July 17, 1996, GCP-Guidelines, the relevant national laws and applicable regulatory requirements. These documents state that the informed consent of the patients is an essential precondition for participation in the clinical study.

